IRB00094234

NCT05759338

23MAY2024

Revian LED Cap

Study Title: A Pilot Study of Revian Red All LED cap as a novel treatment for Central Centrifugal Cicatricial Alopecia.

Principal Investigator, Co-investigator(s): [name], [name], [name], DO

Sponsor or funding source: None

Background, Rationale and Context

Significance

Central centrifugal cicatricial alopecia (CCCA) is a form of scarring hair loss that predominately affects middle-aged women of African descent.¹ The etiology remains unknown; however, inflammatory mediated destruction of the hair follicles is involved in the pathogenesis. Clinically, the natural progression of CCCA starts at the crown as roughly circular scarred patches, which evolve into scarred areas increasing in size circumferentially. Characteristically, the scar is often smooth and shiny, and the hair density in the affected area is frequently decreased. The hair remaining in the scarred areas is more brittle and shorter than the hair in unaffected areas. Since CCCA is a scarring disorder, it can cause permanent hair loss, dyesthesia, and psychological distress which can affect overall quality of life. Affected individuals may complain of pruritus, pain, or tenderness.²

The management of CCCA is challenging due to limited current treatments and a lack of randomized controlled trials. Management focuses on behavioral and styling modifications, in addition to symptomatic relief. Any potentially damaging hair care practices such as chemical relaxers, heat application to the scalp, and the use of hardening gels and sprays are discouraged.³ Many commonly used therapies are anti-inflammatory in nature, including intralesional steroids, topical steroids, oral antibiotics and increased frequency of hair washing with antidandruff shampoos.⁴ These treatments not only lead to improvement in pruritus and tenderness, but in some cases result in increased hair density.⁵ Since there is limited investigation done to determine the most effective treatment approach for CCCA subjects, it would be of great benefit to determine if there is any advantage in using one particular anti-inflammatory therapy over others and whether one is more efficacious in relieving symptoms or promoting hair regrowth in follicles that have not yet become scarred.

The Revian Red All LED cap is a dual-band LED light therapy wireless “smart” cap. It has been shown to be effective in androgenetic alopecia (used once daily, 10-minute treatment regimen) for both men and women. Though no head-to-head comparisons have been done, cross-study comparisons suggest it may provide greater improvements in hair density than low level red laser devices, topical minoxidil and finasteride.⁶ The cap emits two wavelengths of light, 620nm and 660nm, that lead to the production of nitric oxide in the scalp. This increased nitric oxide helps to locally promote blood flow, reduce dihydrotestosterone (DHT), and decrease inflammation.⁶ There are also reportedly minimal side effects, unlike with topical minoxidil which can cause pruritus and initial hair shedding in the first few weeks, or finasteride which can cause gynecomastia and loss of libido. In this study we hope to see if the anti-inflammatory capabilities of this cap can improve scalp symptoms, reduce hair loss, and promote maturation of vellus and intermediate hairs in non-scarred areas of the scalp in those affected by CCCA.

Objectives

The purpose of this study is to determine if the Revian Red All LED cap shows potential to be an effective treatment for CCCA by recruiting hair follicles back to anagen growth or by improving inflammation. The

primary outcome is to determine if hair loss regression is halted. Secondary outcomes include hair regrowth and alleviation of signs and symptoms of the disease.

Methods and Measures

Design

23 subjects who are willing to participate in a novel treatment for Revian Red All LED cap will be enrolled in this study. The cap uses two wavelengths of light, 620 nm and 660 nm. A study cap will be provided for each subject. Subjects will use the cap once daily, 10-minute treatment regimen which is the current androgenetic alopecia recommendation. The subjects will use the cap for a total of 6 months. To use the cap, subjects will connect the Revian Red All LED cap to a Smart App on a mobile phone device using Bluetooth. Subjects can use the Smart App to set daily reminders to use the cap, track and log usage, and use the 10 minute timer. No additional information will be stored on the Smart App. Only subjects will have access to the Smart App located on their personal mobile phone device.

Standardized photos and trichoscopic photos before starting treatment and every 2 months for x 6 total months will be taken to assess hairline stabilization and potential for regrowth. A baseline photo and completion photo will also be taken with a visio device. This will help determine pigmentation of the present hairs throughout the study.

Prior to study enrollment, all participants will receive a detailed explanation of the purpose of the study and will undergo written informed consent. Clinical history of hair loss and history of prior treatment will be obtained by administering a standardized questionnaire to all subjects. Subjects will also fill out a questionnaire regarding symptoms of their hair loss at each visit. There will be 4 visits total (1 Pre-treatment visit and 3 Follow up visits). In order to be eligible, subjects must be diagnosed clinically and histologically with CCCA. Diagnosis will be made only by a board-certified dermatologist.

Setting

This study will be conducted at the Wake Forest Baptist Health Department of Dermatology, [name].

Subjects selection criteria

• Inclusion Criteria

- Women who are between the age of eighteen years and sixty-five years with a biopsy-proven diagnosis of CCCA Stage II-IV. They also must be on stable treatment without changes (on doxycycline, topical steroids, minoxidil and/or post 8 rounds of intralesional steroids) for at least 3 months.
- Subjects will be recruited from outpatient dermatology clinics at the Wake Forest Baptist Health Department of Dermatology.

• Exclusion Criteria

- Subjects with other forms of hair loss that is not CCCA
- Prior treatment with light source for alopecia
- Males are excluded from this study since the prevalence of CCCA in males is so significantly low that it is difficult to find cases in a clinical setting

• Sample Size

We anticipate enrolling 23 subjects in order to assess the effect of Revian Red All LED cap.

Interventions and Interactions

Each subject will have a clinical assessment of hair loss by the investigator at the start of the enrollment and every 2 months until the study is completed. Clinical signs and symptoms of CCCA will be documented by administering a standardized questionnaire to all subjects. Subjects will complete the standardized questionnaire regarding symptoms of their hair loss at the start of the enrollment and every 2 months until the study is completed. Standardized camera and dermatoscopic photographs of the scalp will be obtained at the start of the enrollment and every 2 months until the study is completed.

Total Visits (4)

- Visit 1 (Pre-treatment Visit)
- Visit 2 (Follow Up Visit, 2 months after Visit 1)
- Visit 3 (Follow Up Visit, 4 months after Visit 1)
- Visit 4 (Follow Up Visit, 6 months after Visit 1)

Subjects will use the Revian Red All LED cap, once daily for 10 minutes for a total of 6 months. Subjects will also be called every 2 weeks to verbally confirm consistent use of the cap

Outcome Measure(s)

The main outcome measure in this study is hairline stabilization and/or regrowth, as measured by standardized photography, after Revian Red All LED cap treatment. Secondary outcomes include patient assessment of stabilization and hair regrowth and reduction of signs and symptoms, if present.

Analytical Plan

We expect to be able to enroll 23 subjects in this study. Descriptive statistics such as mean, standard deviation, and range for demographics and subject characteristics at baseline will be obtained. Severity and extent of scalp involvement of CCCA will be assessed by two measures. The first measure will be scoring of symptoms obtained from two questionnaires given to subjects (Appendix I and II). One questionnaire will be given before treatment begins, and the second questionnaire will be given at the start of each subsequent follow up visit (visits 2 and 3) and at the follow-up visit (visit 4). Pre and post-treatment photographs will also be assessed to determine if further scalp hairline recession is present and to look for hair regrowth. The estimates obtained from the subjects' and physicians' questionnaires (Appendix III) will help in designing a larger, randomized clinical trial. Given the small number of subjects, this study is not powered to test for statistical significance; the study will provide the estimate of baseline scores as well as an estimate of change in scores from baseline.

Risk and Benefits

Risks

Possible risks could include mild discomfort, skin irritation, or temporary erythema at the site of the scalp where the cap is applied. However, most subjects do not experience any side effects

Benefits

Subjects may or may not receive any direct benefit from their participation. Subjects may have improvement of their hair loss, either by regrowth of hair or by cessation/stabilization of hair loss. Subjects will be contributing to the general scientific knowledge of potential alternative treatments for hair loss with laser therapy, which may be beneficial to the general population in the future.

Human Subjects Protection

This study does not specifically involve subjects who are particularly vulnerable to coercion or undue influence, including pregnant women, prisoners, medical students, and children.

Subject Recruitment Methods

Subjects will be recruited at the Wake Forest Dermatology clinic. We may also use the Translational Data Warehouse or Epic Electronic Health Records in order to identify subjects that may have been seen in the Dermatology Clinic before with FFA for upcoming appointments. Subjects who meet the criteria mentioned above will be told about the study by either their physician or one of the study investigators. They will be asked about their willingness to participate after completion of their regular visit. This process will continue until 5 CCCA subjects have been recruited. Study data will be kept secure on a password-protected network drive.

Informed Consent

Signed informed consent will be obtained from each subject by one of the physicians in the Wake Forest Dermatology Clinic or by one of the study investigators. Subjects will be recruited from regular clinic visits. Consent will be obtained after their regular clinic visit is complete.

Confidentiality and Privacy

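### The symptom outcome applies only where symptoms are present, but the Analytical Plan does not say how subjects with a baseline score of 0 enter the change estimate

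*Combined protocol and SAP*

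**What the plan says.** Alleviation of signs and symptoms is a secondary outcome under Objectives. Outcome Measure(s) words it conditionally, as "reduction of signs and symptoms, if present". Symptoms are marked on separate 0-10 lines for itch, pain, burning and bumps (Appendices I and II), and Interventions and Interactions has every subject complete the questionnaire.

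The Analytical Plan declares the study not powered for significance testing and says that "the study will provide the estimate of baseline scores as well as an estimate of change in scores from baseline". It adds that the questionnaire estimates are meant to help design a larger randomized trial. It names no analysis set for the symptom scores.

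Entry is for women "with a biopsy-proven diagnosis of CCCA Stage II-IV" who "must be on stable treatment without changes (on doxycycline, topical steroids, minoxidil and/or post 8 rounds of intralesional steroids) for at least 3 months". No criterion mentions a symptom or a minimum score. Under Significance, the protocol says only that affected people may report symptoms. It describes the common anti-inflammatory therapies as "including intralesional steroids, topical steroids, oral antibiotics and increased frequency of hair washing with antidandruff shampoos" and says of them: "These treatments not only lead to improvement in pruritus and tenderness".

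**The concern.** The outcome is conditional and the analysis is not. A subject at 0 on a scale cannot improve on it. Because there are four scales, someone with itch alone is at the floor on the other three. If such subjects enter a single mean change, the result mixes change in people who had the symptom with zeros, or increases, from people who did not.

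This matters more than it would in a trial built around a test. The pilot disclaims testing, so its estimates are its product, and they are to be carried into the planning of a randomized trial. A reader given one mean change could not tell small relief in most subjects from larger relief in a few. A baseline mean, standard deviation and range would not settle it either, because they give neither the number at 0 nor the change among the rest.

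**Working it through.** The plan states no effect size, standard deviation, power or share at 0, so there is no figure of its own to reproduce.

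**Inputs from the documents.** N = 23 (Design, Sample Size, Analytical Plan); scale floor of 0 (Appendices I and II); no symptom required at entry; outcome conditional on presence; no analysis set.

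**Assumed, not in the documents.** k = number at 0 at Visit 1, taken as 6, 12 or 17; d = mean improvement in subjects above 0, taken as 2 points; s = standard deviation of that improvement, taken as 2 points. Subjects at 0 stay at 0 unless stated. Improvement is shown as positive.

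**Formulas.** With m = N − k:
- All-subject mean: M = d × m/N.
- All-subject SD: √{[(m − 1)s² + m(d − M)² + kM²]/(N − 1)}.
- 95% interval: M ± t(N − 1) × SD/√N. For the subset: d ± t(m − 1) × s/√m.

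**Worked case, k = 12, m = 11.** M = 2 × 11/23 = 0.96. The sum of squares is 10 × 4 + 11 × 1.04² + 12 × 0.96² ≈ 63, so SD = √(63/22) = 1.69. The half-width for N = 23 is 0.432 SD = 0.73, which gives 0.22 to 1.69.

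| At 0 | Factor m/N | All-subject mean (95% CI) | Subset above 0 (95% CI) |
|---|---|---|---|
| 0 | 1.00 | 2.00 (1.14 to 2.86) | 2.00 (1.14 to 2.86) |
| 6 | 17/23 = 0.74 | 1.48 (0.64 to 2.31) | 2.00 (0.97 to 3.03) |
| 12 | 11/23 = 0.48 | 0.96 (0.22 to 1.69) | 2.00 (0.66 to 3.34) |
| 17 | 6/23 = 0.26 | 0.52 (−0.04 to 1.09) | 2.00 (−0.10 to 4.10) |

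The factor m/N does not depend on d or s; the intervals do.

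**If those at 0 worsen by 0.5 on average.** The mean becomes (2m − 0.5k)/23, that is 1.35, 0.70 or 0.15 for k = 6, 12 or 17.

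**What the subset costs.** Suppose each subject scores 3 at a random half of visits and 0 otherwise, and the cap does nothing. The all-subject change is 0 on average. Subjects chosen for a baseline above 0 start at 3 and average 0.5 × 3 = 1.5 later, an apparent improvement of 1.5 points from selection alone. Neither summary is sufficient without the other.

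**The case against.** The strongest reply is that this is a secondary outcome in a descriptive pilot, that the photographic main outcome is untouched, and that which population to summarize is partly a matter of preference. Requiring stable background treatment is also sensible, since it limits confounding by treatment changes. All of this stands and keeps the point modest. It does not supply the missing rule.

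Four stronger readings are tempting, and the documents do not support them.

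- *That the plan estimates change over everyone.* Pooling is the natural default, because all subjects complete the scales and no subset is named. But the Analytical Plan does not say so, and Outcome Measure(s) points the other way. The finding is silence, not a stated choice to pool.
- *That every subject is on symptom-relieving treatment.* The options are joined by and/or, so minoxidil alone qualifies. It is not among the therapies credited with relief, and the protocol refers to "topical minoxidil which can cause pruritus and initial hair shedding in the first few weeks". The relief claimed is of pruritus and tenderness, not of burning or bumps. That many subjects will score 0 is therefore plausible but not shown.
- *That relief would be hidden.* In the illustration, relief is still visible with 12 of 23 at 0, and with 17 at 0 both intervals cross 0. Hiding needs a more extreme case: with d = 3 and 18 of 23 at 0, the all-subject interval is −0.01 to 1.31 against 0.52 to 5.48 in the subset.
- *That a later trial would be about four times too large.* That figure needs an assumed half of subjects at 0, an assumed change of 3 with SD 2, an uncontrolled change used as a between-arm effect, and a later trial limited to symptomatic subjects. The documents state none of these. If the later trial enrols the same mixed population, the all-subject figures are the relevant planning inputs.

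The objection that a baseline-above-0 subset brings regression to the mean is correct. It is why that subset should stand beside the all-subject change and not replace it.

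**Conclusion.** The point holds as a gap between outcome and analysis. The condition in Outcome Measure(s) has no counterpart in the Analytical Plan, and the entry criteria allow subjects for whom a symptom is absent. If all subjects are pooled and those at 0 stay there, the mean change shrinks by exactly the share at 0, and by more if some of them worsen. The factors 0.74, 0.48 and 0.26 follow from the assumed counts of 6, 12 and 17 out of 23. The true count on any scale is not in the documents, so the dilution could be negligible or large. The main outcome is not affected. This is an inexpensive clarification worth making before the symptom data are summarized, not a flaw that undermines the study.

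**What to change.** Add to the Analytical Plan, for each of the four symptom scales:

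1. The number of subjects scoring 0 at Visit 1.
2. Change from baseline to Visits 2, 3 and 4, side by side for all subjects and for subjects with a baseline score above 0, each with its number of subjects and a 95% confidence interval.
3. Among subjects at 0 at Visit 1, the number with a new symptom at each later visit.
4. A statement that the subset has fewer subjects, that its change is subject to regression to the mean, and that with no control arm it must not be read as an effect of the cap.

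The cost is a few sentences and some extra table rows. The data are already to be collected, and eligibility and the visit schedule do not change. The price is precision: in the illustration the subset interval widens from 0.97 to 3.03 with 17 subjects to 0.66 to 3.34 with 11.

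The enrolment target should be reconciled at the same time. Design and Sample Size give 23, while Subject Recruitment Methods stops at 5 and Appendices I and II number subjects 1 to 5. The 95% half-width for a mean change is 0.43 SD with 23 subjects and 1.24 SD with 5. At 5, a symptomatic subset would be too small to use.

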Appendix I: Pre-Treatment Questionnaire for subjects

Subject Study Number: _____ (will be 1-5 in the order of enrollment)

1. What is your date of birth? _____ (mm/dd/yyyy)
2. Which one choice best describes your race? (Please choose only one answer)

_____ Black or African American

If Black or African American is checked, is your ethnic background:

_____ African

_____ Caribbean

_____ Other Black or African descent

_____ Mixed race (Black or African American + Other)

3. What is your ethnicity? (PLEASE CHECK ONLY ONE)

Hispanic or Latin origin
 Non-Hispanic or Non-Latin origin
 Unknown

Hair Loss History

4. When did you first notice your hair loss? _____ / _____ (month/year)
5. How many dermatologists did you consult for the hair loss on the crown of scalp before a diagnosis of central centrifugal cicatricial alopecia (CCCA) was made? _____
6. Have you been given any type of medical treatment for your vertex hairline recession?
Yes No

[figure not shown]
If yes, please check all medications that you used for a time period of AT LEAST 3 MONTHS and indicate the effect of each treatment on your hair loss by placing an X in the appropriate box.

Treatment Used	Response			
	Regrowth	Prevented further loss	Did not stop loss	Do not know
 Oral Steroid (e.g. Prednisone)				
 Intralesional (injection into the scalp) steroids				
 Topical steroids (clobetasol, halobetasol, fluocinolone, betamethasone dipropionate, triamcinolone, fluocinonide, mometasone)				
 Hydroxychloroquine (Plaquenil®)				

[figure not shown]
 Methotrexate				
 Mycophenolate (Cellcept®)				
 Cyclosporin (Neoral®, Sandimmune®)				
 Topical imiquimod (Aldara®)				
 Spironolactone (Aldactone®)				
 Finasteride (Propecia®, Proscar®)				
 Dutasteride (Avodart®)				
 Tetracycline antibiotic class (e.g. Tetracycline®, Doxycycline®, Minocycline® etc.)				
 Topical tacrolimus (Protopic®)				
 Pioglitazone (Actos®)				
 Azathioprine (Imuran®)				
 Topical minoxidil (Rogaine®)				
 Hair transplants in area of hair loss				
 Other: _____				

Symptoms

[figure not shown]

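### Recruitment is written to stop at 5 subjects and both questionnaires number subjects only 1 to 5, but the protocol plans 23

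*Combined protocol and SAP*

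**What the plan says.** Three sections of the combined protocol and SAP give 23:

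- Design: "23 subjects who are willing to participate in a novel treatment for Revian Red All LED cap will be enrolled in this study".
- Sample Size, under the selection criteria: "We anticipate enrolling 23 subjects in order to assess the effect of Revian Red All LED cap".
- Analytical Plan: "We expect to be able to enroll 23 subjects in this study".

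Three places give 5:

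- Subject Recruitment Methods, under Human Subjects Protection: "This process will continue until 5 CCCA subjects have been recruited".
- Appendix I, the pre-treatment questionnaire, beside the study-number field: "will be 1-5 in the order of enrollment".
- Appendix II, the follow-up questionnaire, which carries the same note.

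On purpose, the Analytical Plan says that "this study is not powered to test for statistical significance" and that "the study will provide the estimate of baseline scores as well as an estimate of change in scores from baseline". The questionnaire estimates "will help in designing a larger, randomized clinical trial".

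**The concern.** The two sets of passages cannot both be followed. A coordinator working from the recruitment section closes enrolment after the fifth subject. A coordinator working from the Sample Size section continues to 23, contrary to the recruitment section, and runs out of permitted study numbers at the sixth subject. The numbering matters because the Confidentiality section makes the unique study identifier the only identifier on the data collection form.

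Either course leaves part of the protocol unfollowed, and the protocol requires deviations to be reported promptly to the IRB. If the lower figure governs, the pilot also loses most of the precision of the estimates it exists to produce.

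**Working it through.** **1. Can 23 be reproduced?** No. The protocol gives no alpha, power, effect size, SD or dropout rate, so no sample-size formula applies. The check is therefore one of consistency, followed by the consequence for precision.

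**2. Size of the gap.** 5/23 = 0.217, or 21.7% of the plan. The shortfall is 23 − 5 = 18 subjects.

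**3. Could the two figures describe different things?**

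- *Dropout:* both figures count subjects recruited or enrolled, not completers. Going from 23 to 5 would in any case need a loss of 1 − 5/23 = 78%.
- *Site quota:* the Setting section names a single department.
- *Stage or interim step:* none is described.
- *Superseded text:* the document contains no amendment log, and all six statements are current.

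**4. Precision of a mean change from baseline.** The 95% half-width in SD units is t(0.975, n−1)/√n.

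- n = 23: 2.074/4.796 = 0.43 SD
- n = 5: 2.776/2.236 = 1.24 SD

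The ratio is 1.2417/0.4324 = 2.87.

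**5. Precision of the SD itself**, which a later trial would use for its sample size. The 95% limits, as multiples of the estimated SD, are √((n−1)/χ²) at the 0.975 and 0.025 quantiles with n−1 degrees of freedom.

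- n = 23: √(22/36.78) = 0.77 and √(22/10.98) = 1.42
- n = 5: √(4/11.14) = 0.60 and √(4/0.4844) = 2.87

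A sample size for a mean is proportional to SD squared. At the upper limit, a later trial sized on the pilot's SD could therefore be too small by a factor of 22/10.98 = 2.0 with 23 subjects, or 4/0.4844 = 8.3 with 5.

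**6. Illustration for a yes/no finding.** If none of n subjects has a given event, the exact two-sided 95% upper limit is 1 − 0.025^(1/n): 14.8% for n = 23 and 52.2% for n = 5.

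Steps 4 and 5 need no assumed SD. They do assume roughly normal change scores and that every enrolled subject is analysed.

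**The case against.** The strongest reply is that 5 is stale text and nobody would act on it. Three sections agree on 23, one of them the dedicated Sample Size section. The recruitment paragraph also searches records for patients with FFA, an abbreviation that the protocol does not define and uses nowhere else, which suggests carried-over wording. On that reading the likely result is a 23-subject study with a paperwork deviation, and the n = 5 figures describe something that will not happen. This is plausible, but the documents do not say that 5 is superseded, and it recurs on two working forms. A leftover in a recruitment rule still has to be corrected.

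Four narrower points stand:

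- The questionnaires state no enrolment target. They cap the subject number at 5, which implies that total. Only the recruitment sentence actually stops enrolment.
- The SD-based figures suit the 0–10 symptom scales and the DLQI. They do not suit the photographic main outcome or the clinician's mild/moderate/severe grades.
- The zero-event limit is illustrative, since the plan defines no such event.
- Even 23 subjects leave a possible 2.0-fold understatement of a later sample size, so 23 is better but not precise.

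That the study is unpowered is no defence: the point concerns precision and conduct, not power.

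**Conclusion.** The concern holds, and the text must be corrected. The planned sample size is contradicted by the only rule that ends recruitment and by the numbering on both subject forms. Read literally, that rule delivers 21.7% of the planned sample and widens the confidence interval for a mean change 2.87-fold.

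The contradiction rests on the text alone and needs no assumption. The loss of precision arises only if recruitment really stops at 5. If it continues to 23, the consequence is instead a departure from the written recruitment rule and from the form numbering for 18 subjects.

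**What to change.** The sponsor should first confirm that 23 is the intended number, since the protocol gives no derivation for it. Then:

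1. In Subject Recruitment Methods, change the recruitment limit from 5 to 23 CCCA subjects.
2. In Appendices I and II, extend the study-number range from 1–5 to 1–23.
3. Preferably, state under Sample Size the precision that 23 gives: a 95% half-width of about 0.43 SD for a mean change in a score, if all 23 are analysed. This is not needed to resolve the contradiction, but it gives 23 an explicit basis where no power is claimed.

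The cost is one corrected sentence and two form headers, with one added sentence if step 3 is taken, through a minor IRB amendment. The consent form was not available for this review, so any enrolment number it states should be checked at the same time. No subjects are added beyond the 23 already planned.
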